5. PATIENT SELECTION & ELIGIBILITY

- 5.1. Patient must be 18 years of age.
- 5.2. Histologically proven prostate adenocarcinoma

- 5.2.1. Gleason score 2-7 (reviewed by reference lab) if initial pathology differs from that of reference lab, reference lab's interpretation will be used for eligibility and risk group assignment
- 5.2.2. Biopsy within one year of date of registration
- 5.3. Clinical stage T1b-T2b, N0-Nx, M0-Mx (AJCC 6th Edition)
 - T-stage and N-stage determined by physical exam and available imaging studies (ultrasound, CT, and/or MRI; see section 4.5)
 - 5.3.2. M-stage determined by physical exam, CT or MRI. Bone scan not required unless clinical findings suggest possible osseous metastases.
- 5.4. PSA 20 ng/ml (if pre-enrollment PSA was drawn >60 days prior to CyberKnife treatment, another PSA, obtained 60 days prior to treatment, will become the pre-treatment PSA, and will determine eligibility and risk group; pre-treatment PSA must be drawn 30 or 90 days after discontinuing finasteride or dutasteride respectively)
- 5.5. Patients belonging in one of the following risk groups:
 - 5.5.1. Low: CS T1b-T2a and Gleason 2-6 and PSA 10, or
 - 5.5.2. Intermediate: CS T2b and Gleason 2-6 and PSA 10, or CS T1b-T2b, and Gleason 2-6 and PSA 20 ng/ml, or Gleason 7 and PSA 10 ng/ml
- 5.6. Prostate volume measurement:
 - 5.6.1. Determined using: volume = $\frac{6}{6}$ x length x height x width
 - 5.6.2. Measurement from CT or ultrasound 6 months prior to registration or 14 days prior to registration if hormone therapy given; if patient had taken finasteride or dutasteride, volume determined >30 or >90 days (respectively) after discontinuation.
- 5.7. ECOG performance status 0-1
- No prior prostatectomy or cryotherapy of the prostate
- No prior radiotherapy to the prostate or lower pelvis
- 5.10. No implanted hardware or other material that would prohibit appropriate treatment planning or treatment delivery, in the investigator's opinion.
- No chemotherapy for a malignancy in the last 5 years.
- 5.12. No history of an invasive malignancy (other than this prostate cancer, or basal or squamous skin cancers) in the last 5 years.
- 5.13. No hormone ablation for two months prior to enrollment, or during treatment. This includes LHRH agonists (e.g. leuprolide,goserelin, triptorelin) and antagonists (e.g. degarelix), peripheral blockers (e.g. flutamide, bicalutamide, nilutamide), estrogens (e.g. DES), bilateral orchiectomy, and 5-alpha reductase inhibitors (finasteride or dutasteride).
- 5.14. Completion of patient questionnaires in section 4.7.
- 5.15. Consent signed.

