17.0 References

PROSPECTIVE EVALUATION OF CYBERKNIFE STEREOTACTIC RADIOSURGERY FOR LOW AND INTERMEDIATE RISK PROSTATE CANCER: EMULATING HDR BRACHYTHERAPY DOSIMETRY

SCHEMA

PATIENT POPULATION (see section 4.0 for complete eligibility)

Histologically-confirmed, adenocarcinoma of the prostate

Clinical Stage T1b - T2b, NX-0, MX-0

One of the following combinations:

- Gleason score 2-6 and PSA 20
- Gleason score 7 and PSA 10

ECOG Performance Status 0-1

No prior prostate radiation or other definitive therapy

Required sample size: 253

ELIGIBILITY CHECKLIST

(Y)	Is there histologically proven prostate adenocarcinoma, biopsy within one year of enrollment?
(2-6)	What is the Gleason Score?
(T1b - T2b)	What is the clinical T-stage? (AJCC 6 th Edition)
(Y)	Is the patient clinical Nx or N0, and Mx or M0?
(0-20)	What is the patient's PSA?
(L, I)	Does the patient fall into one of these risk groups (AJCC 6 th Edition): - Low: CS T1b-T2a, Gleason 2-6, PSA 10 - Intermediate: CS T2b, Gleason 2-6, PSA 10, or CS T1b-T2a, and Gleason 2-6, PSA 20 ng/ml, or Gleason 7, PSA 10 ng/ml
(0-1)	What is the ECOG performance status?
(N)	Has the patient undergone prostatectomy or cryotherapy of the prostate?
(N)	Has the patient had radiotherapy to the prostate or lower pelvis?
(N)	Is there implanted hardware near the planning target volume that would prohibit appropriate treatment planning or treatment delivery in the investigator's opinion?
(N)	Has the patient had chemotherapy for a malignancy in the last 5 years?
(N)	Has the patient had an invasive malignancy (other than this prostate cancer, or basal or squamous skin cancers) in the last 5 years?
(N)	Has the patient's androgen function been ablated during the past 2 months?

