4. PRETREATMENT EVALUATION

- 4.1. Complete history and physical exam
- 4.2. DRE findings
- 4.3. Assessment of performance status
- 4.4. Histological evaluation of prostate biopsy with assignment of Gleason score
- 4.5. Evaluation of the pelvic lymph nodes with CT or MRI is optional
- 4.6. Serum PSA. Laboratory evaluation must be done within 90 days prior to registration, or <60 days prior to hormone therapy, and 30 or 90 days after discontinuing finasteride or dutasteride, respectively.
- 4.7. CBC, platelets, serum BUN, creatinine and testosterone; may be drawn after registration
- 4.8. Transrectal ultrasound volume study of the prostate or a digital rectal exam (DRE) will be performed prior to enrollment to verify the prostate volume. The prostate volume may be obtained by step section summated measurements at 5 mm intervals through the entire gland (stepping method) or the by the length-width-height method. An MRI-based prostate volume measurement will also be acceptable (specify which modality).
 - 4.8.1. Measurement from CT or ultrasound 6 months prior to registration, or 14 days prior to registration if hormone therapy given; if patient had taken finasteride or dutasteride, volume determined >30 or >90 days (respectively) after discontinuation.
- 4.9. Patient should be able to complete questionnaires (see Appendix VI), baseline questionnaires may be completed before or after enrollment, but before treatment)
 - 4.9.1. SF-12 questionnaire
 - 4.9.2. AUA questionnaire
 - 4.9.3. EPIC-26 questionnaire
 - 4.9.4. SHIM questionnaire
 - 4.9.5. Utilization of Sexual Medications/Devices questionnaire

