9.1. EVALUATION DURING TREATMENT & FOLLOWING TREATMENT

- 9.1.1. PRE-ENTRY ASSESSMENT: see section 4.7.
- 9.1.2. Stereotactic radiosurgery is an outpatient procedure. Patient management immediately after the procedure will follow routine patient care guidelines as determined by the physician. Subjects will be provided instructions on who to call with specific contact information, in the event they experience any untoward effects following treatment. In the event a subject experiences any untoward effects following CyberKnife treatment, information specific to the patient's condition and symptoms, treatment intervention required, and hospital stay and course will be recorded for purposes of clinical evaluation.
- 9.1.3. ACUTE ASSESSMENT: Patients will have toxicity evaluation and AUA score on the last day of treatment.
- 9.1.4. ASSESSMENTS FOLLOWING TREATMENT: at one week after treatment (allowed window: +/- 3 days), toxicity and AUA score will be evaluated. At 1 month (+/- 7 days) following treatment, patients will be assessed for acute toxicity, and will fill out AUA form, SF-12, EPIC-26, SHIM and Utilization of Sexual Rx/Devices. At 3, 6, 12, 18, and 24 month (+/- 2 wks) intervals (and every 6 months thereafter, through year 5), patients will be seen and evaluated, including a history, physical exam, ECOG performance status, PSA, toxicity evaluation, and AUA score. In addition, at 6 months, 12 months and annually thereafter, the SF-12, EPIC-26, SHIM and Utilization of Sexual Medications/Devices will be administered. After the 5 year follow-up patients will be seen yearly through year 10 (allowed window: +/-1 month) and the following will be performed: PSA, toxicity evaluation, and the following questionnaires will be administered: EPIC -26; AUA; SHIM. Examination and studies may

- be done at outside facility. A serum total testosterone will be measured at baseline and with every PSA through year 2.
- 9.1.5. PROSTATE BIOPSY will be performed at time of biochemical or local clinical failure, and is encouraged at 2 years following treatment and at time of distant failure.
- 9.1.6. BONE SCAN will be performed at the time of biochemical failure, or when the patient develops signs of symptoms suggesting metastatic disease.
- 9.1.7. Axial Imaging (CT or MRI) of the abdomen and pelvis will be performed at the time of biochemical failure, or when the patient develops signs of symptoms suggesting metastatic disease.

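### For men with earlier androgen deprivation, Section 5.4 lets a PSA drawn after hormones replace the pre-hormone value that sets eligibility and risk group

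*Combined protocol and SAP*

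**What the plan says.** The relevant rules are spread over several sections of the combined protocol and SAP.

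- Section 5.13 excludes recent hormone use only: "No hormone ablation for two months prior to enrollment, or during treatment". It lists LHRH agents, peripheral blockers, estrogens, orchiectomy and the two 5-alpha reductase inhibitors. Earlier use is not excluded.
- Section 4.6 foresees men who have had hormones and times their PSA by the start of that therapy: "Laboratory evaluation must be done within 90 days prior to registration, or <60 days prior to hormone therapy".
- Section 5.4 applies when the pre-enrollment PSA is more than 60 days old at treatment: "another PSA, obtained 60 days prior to treatment, will become the pre-treatment PSA, and will determine eligibility and risk group". Its washout covers two drugs: "pre-treatment PSA must be drawn 30 or 90 days after discontinuing finasteride or dutasteride respectively".
- Sections 4.8.1 and 5.6.2 also foresee hormone-treated men. They time the prostate volume measurement "14 days prior to registration if hormone therapy given".
- The Eligibility Checklist asks: "Has the patient's androgen function been ablated during the past 2 months". It does not name 5-alpha reductase inhibitors.
- Section 4.7 covers the baseline bloods: "CBC, platelets, serum BUN, creatinine and testosterone; may be drawn after registration". Section 9.1.4 adds: "A serum total testosterone will be measured at baseline and with every PSA through year 2". No eligibility criterion and no bDFS definition uses the testosterone result.

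**The concern.** Section 4.6 keeps the pre-hormone PSA usable, which is the value that reflects the untreated disease. Section 5.4 then gives the decision to a later PSA and sets no washout for the drugs most directly aimed at androgen. A man with Gleason 6 and stage T2a is separated from the intermediate group, or from ineligibility, by PSA alone. For him the choice of PSA is the choice of risk group.

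Two things follow. First, risk group determines seminal vesicle coverage and the posterolateral margin (8.3.3), so a misassigned man is planned under the other group's rules. Second, it determines the recorded case mix. The text after Table 1 predicts 94% bDFS from a 70/30 mix and says the rate required for success may need adjusting if the mix departs from that. Mislabelled men would hide such a departure.

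The primary endpoint is also defined by PSA (2.0, 9.4.1). Some men may still be suppressed at entry, and nothing in the bDFS rules takes account of it.

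**Working it through.** **Does 5.4 always displace the pre-hormone PSA?** Take enrollment as day 0.

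1. Under 5.13, hormones stopped on or before about day -60.
2. The pre-hormone PSA precedes the start of hormones, so it is earlier still.
3. Treatment comes after enrollment. Planning imaging also waits at least 7 days after fiducial placement (8.2.1).
4. The pre-hormone PSA is therefore always more than 60 days old at treatment, and 5.4 always calls for a new one.

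This does not depend on the comparison sign that appears to have dropped out before the 60 days in 5.4.

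**How long off hormones is the replacement PSA?** Read 5.4 as within 60 days before treatment, with treatment T days after enrollment. The earliest draw is day T - 60. A man who stopped on day -60 is then (T - 60) + 60 = T days off hormones: 30 days if T = 30, and 90 days if T = 90, the limit in 6.2. The two-month rule in 5.13 does not guarantee two months off at the draw. For comparison, 5.4 asks for 90 days after dutasteride.

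**The plan's own sample size (11.3).** With p0 = 0.90, p1 = 0.945, Z = 1.645 and 0.84:

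N = [0.84 x sqrt(0.945 x 0.055) + 1.645 x sqrt(0.90 x 0.10)]^2 / 0.045^2 = 231.7, so 232. Then 232/0.92 = 252.2, so 253. Both figures reproduce.

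**The success rule (11.4.1) at n = 232.** The lower limit L is 0.8984 at 216 disease-free and 0.9034 at 217. Success therefore needs at least 217 disease-free, that is at most 15 failures. Exact binomial probability of success: 79% at a true 94.5% and 68% at a true 94%.

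**Illustration only.** The documents give no share of affected men. Assume a share s of all men counted as favorable (98%) who really belong to a worse group, using the 5-year rates after Table 1 (82% intermediate, 59% unfavorable). Start from the stated 94%.

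| s | True group | Drop = s x difference | True bDFS | Extra failures in 232 | Chance of success |
|---|---|---|---|---|---|
| 0 | - | 0 | 94.00% | 0 | 68% |
| 2% | intermediate | 0.02 x 0.16 = 0.32 points | 93.68% | 0.7 | 60% |
| 5% | intermediate | 0.05 x 0.16 = 0.80 points | 93.20% | 1.9 | 49% |
| 2% | unfavorable | 0.02 x 0.39 = 0.78 points | 93.22% | 1.8 | 49% |
| 5% | unfavorable | 0.05 x 0.39 = 1.95 points | 92.05% | 4.5 | 24% |

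At s = 0.5% the chance is 66% (intermediate) or 63% (unfavorable). The table covers mislabelling only. It does not model residual suppression or testosterone recovery.

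**The case against.** A reader might infer that still-suppressed men do enter the trial. The documents do not support that as a fact. The checklist wording can be read as asking about a hormonal state and not the date of the last dose, and 5.13 lists orchiectomy under the same rule, which favors that reading. Nor do the documents say how long suppression lasts after any LHRH agent. What stands is that such entry is possible, because no testosterone criterion enforces the state reading.

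A reader might also infer that bDFS is biased in a known direction. It is not. Hidden higher-risk men lower bDFS, residual suppression could delay failure, and PSA rising as testosterone recovers could produce apparent failures. Section 9.4.1.2 partly covers that last case: three rises in the first two years followed by a decline not induced by hormones do not count. The Phoenix definition in 9.4.1.1 has no such clause.

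Section 5.4 could be meant only to keep the PSA current, and 6.2 registers a man only after all criteria are met. If 4.6 is read so that the pre-hormone value governs at registration, a man above 20 ng/ml fails there. This is a fair reading on eligibility, but 4.6 offers alternatives joined by an or, so a post-hormone PSA within 90 days of registration also satisfies it. On risk group the wording of 5.4 leaves no such room.

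Other safeguards limit the harm. Gleason score is set by the reference laboratory (5.2.1), and MRI evidence of T3 disease that the investigator accepts leads to withdrawal from the protocol (8.3.3.1). Neither restores the PSA component.

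The 5-alpha reductase inhibitor windows are not strictly contradictory, since 5.13 limits drug use and 4.6 and 5.4 time a blood draw. Still, a man 61 days off dutasteride meets 5.13 but has no valid PSA until day 90. The eligibility case report forms may name these drugs, but they are not in the documents.

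**Conclusion.** The point holds in a limited form. For men whose LHRH, antiandrogen or estrogen therapy ended more than two months before enrollment, 5.4 replaces the PSA accepted by 4.6 with one drawn after hormones and lets it set the risk group. This follows from the text and date arithmetic alone. Only the PSA component can be misread.

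The size is unknown. The 2-5% share is an assumption, and the 59% rate is the harsher of two, because men hidden on PSA alone would still have T1b-T2b disease and a reviewed Gleason score. The intermediate scenario (60-49%, against 68%) is the more moderate illustration; the unfavorable one (49-24%) marks the severe end. If few enrolled men had earlier deprivation, the effect is negligible. The change is worth making because the rule misassigns a variable that drives target volumes and case mix, and because correcting it is cheap.

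**What to change.** 1. In 5.4 and 5.5, state that for a man with earlier androgen deprivation the pre-hormone PSA accepted in 4.6 sets eligibility and risk group, and that a later PSA cannot lower the group.
2. Reconcile the hormone and 5-alpha reductase inhibitor windows in 4.6, 4.8.1, 5.4, 5.6.2, 5.13 and the checklist row. Which interval applies is for the sponsor to decide.
3. Specify a bDFS sensitivity analysis that excludes or flags men with earlier deprivation, using the testosterone collected at baseline and through year 2. Confirm that the case report forms capture the drug, its dates and the pre-hormone PSA.
4. Leave to the sponsor whether testosterone becomes an entry criterion. The documents define no threshold, and registration is dated at consent (6.2), so the timing of the draw would also need settling.

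Section 11.2 already counts 260 subjects. If enrollment is closed, item 1 can still serve as an analysis rule for reclassifying men when case mix and results by risk group are reported.

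The cost is wording, one extra analysis and possibly some retrieval of pre-hormone PSA values. No new test is needed. The downside is that a few men move to a higher risk group or become ineligible.

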6. REGISTRATION PROCEDURES

PRE-REGISTRATION REQUIREMENTS: Prior to enrolling patients into the study, facilities must complete the Facility Questionnaire, the Benchmark (Dry Run) Treatment Plan (see section 8.3.2.1), and the Physics QA requirements specified below. After review by the Principal Investigator and Physics Chair confirms satisfactory completion, sites are eligible for study participation.

6.1. PHYSICS QUALITY ASSURANCE shall at a minimum include:

- 6.1.1. ABSOLUTE DOSIMETRY: Each site must document CyberKnife absolute calibration in water according to AAPM TG51. Site must also document that, within the last year, photon beam output has been verified by the Radiological Physics Center (RPC).
- 6.1.2. DAILY QA: participating sites must provide documentation that, for the prior month, the following has been performed daily:
 - 6.1.2.1.1. At least 3000 MUs delivered daily for machine warm-up (per Accuray)
 - 6.1.2.1.2. Temperature and atmospheric pressure recorded, output calibration performed, and new output factor recorded.
 - 6.1.2.1.3. Position of laser at perch position verified to be within 1mm of floor reference point.
- 6.1.3. MONTHLY QA: sites must provide documentation that the following monthly QA is being performed:
 - 6.1.3.1.1. Beam output in phantom verified as +/- 1% of specified output
 - 6.1.3.1.2. Beam energy constancy verified by ion chamber measurements at two depths in phantom, using 60mm collimator and 80cm SAD. Ratio should be within +/- 2% of the output ratio determined from TPR tables.
 - 6.1.3.1.3. Beam symmetry measured by water scanning system or by radiographic (XV) or gafchromic (EBT or MD55) film. Beam symmetry should not exceed +/- 2% using area method.
 - 6.1.3.1.4. Fiducial tracking end-to-end tests using ball-cube phantom. Maximum tracking radial error should be <0.95mm, with left-right, ant-post, and inf-sup errors not exceeding 0.8mm.

 - 6.1.3.1.5. Laser radiation field congruence measured using XV or EBT film in phantom under standard conditions (SAD = 80cm, 5mm build-up material and 60mm collimator), with laser center marked by a pin. Displacement, evaluated using imaging software or graph paper, should not exceed 1mm.
- 6.1.4. Daily and monthly QA as described above may be recorded in the CyberKnife Robotic Radiosurgery System QA Log Book, or in other documents, and should continue throughout the enrollment period.
- 6.2. PATIENT REGISTRATION: Patients may be registered only after all eligibility criteria are met: see Eligibility Checklist above, and Inclusion Criteria and Exclusion Criteria CRFs (Case Report Forms). After the patient signs the Consent Form the patient is enrolled in the study, and scheduled for treatment. The pre-treatment CRFs are then filled out by the investigator and/or research assistant. This data is retained in the patient's chart and in research office. The date of registration shall be the date the consent was signed. Fiducials must be placed within 60 days, and the first fraction of radiosurgery must be administered within 90 days of registrations.

7. PATHOLOGY

- 7.1. Pathology Evaluation: Slides/blocks from the pre-treatment diagnostic prostatic biopsy will be reviewed to confirm the diagnosis and Gleason score. Other histopathologic features, including extent of tumor in the biopsies, the number of biopsies positive and perineural invasion, shall be recorded.
- 7.2. Central Review: All consenting patients must have a complete representative set of biopsy slides or tissue block submitted to the Central Pathology Laboratory in order for the case to be evaluated for central pathology review. The following must be provided:

- 7.2.1. A complete representative set of biopsy slides (12 slides) or tissue block. If initial pathology differs from that of reference lab, the reference lab's interpretation will be used for eligibility and risk group assignment
- 7.2.2. A Pathology report documenting the submitted blocks, core or slides contain tumor; the report must include the Accuray protocol number and the patient's case number. The patient's name and/or other identifying information should be removed from the report.
- 7.2.3. Submit materials for central review to Bostwick Laboratory; other central review lab may be used if approved by Sponsor and Principal Investigator.

8. TREATMENT: CYBERKNIFE RADIOSURGERY

- 8.1. FIDUCIAL PLACEMENT: All patients will have gold fiducial seeds measuring 3-5 mm placed in the prostate prior to treatment planning. A minimum of three fiducial seeds will be placed under transrectal ultrasound guidance, using either transperineal or transrectal approach, with local anesthesia and/or sedation as required. The use of linked fiducials are encouraged, since they may migrate less than individually placed fiducials. The physician will place seeds such that they are visible (and not superimposed) on CyberKnife orthogonal imaging, are not collinear, and ideally are separated by 2 cm or more. Fiducials will be placed as an outpatient procedure. Local anesthestic injection, oral or intravenous sedating medication, oral or intravenous pain medication and prophylactic antibiotics may be given at the discretion of the investigator to maximize the safety and comfort of fiducial placement. At least three seeds must be usable for tracking during treatment. If an interim analysis shows unacceptable fiducial migration with a specific technique or type of fiducial, further use of this technique or type of fiducial may be prohibited by the Principal Investigator.
- 8.2. TREATMENT PLANNING IMAGING: The treatment plan will be created based on the risk group assigned by the reference lab review.
 - 8.2.1. To allow fiducial stabilization and resolution of swelling, planning studies will be imaged >= 7 days after fiducial placement. Alpha Cradle or a similar immobilization device will be used as needed.
 - 8.2.2. CT scans will be taken for treatment planning. CT slices will be 1 1.5mm, with 250-512 slices taken centered at the prostate. The imaging sets will be downloaded to the CyberKnife treatment planning system to develop the radiosurgery treatment plan.
 - 8.2.3. If not medically contraindicated, all patients will undergo MRI imaging to determine the anatomical borders of the prostate. This study will be fused to the treatment planning CT. No endorectal coil allowed.
 - 8.2.4. URETHRAL IDENTIFICATION:
 - 8.2.4.1. The planning CT and MRI scans will be done with a Foley catheter in place to define the course of the urethra through the CTV. To improve comfort and minimize inconvenience to the patient, if possible, CT and MRI planning studies will be done consecutively. The smallest possible Foley catheter will be used.
 - 8.2.5. Prior to treatment planning imaging, the patient will follow the bowel/urinary preparation procedures used for treatment (see section 8.4.2).

8.3. CYBERKNIFE TREATMENT PLANNING:

8.3.1. TREATMENT PLANNING PROCEDURES: Inverse planning using the CyberKnife planning system will be employed. The treatment plan used for each treatment will be based on an analysis of the volumetric dose including dose-volume histogram (DVH) analyses of the PTV and critical normal structures. Any beams entering through a hip prosthesis on their way to the planning target volume shall be turned off. Number of paths and beams used for

each patient will vary and will be determined by the selected individual treatment plan. A priority will be placed on reducing overall treatment time, number of non-zero beams and total monitor units without compromising the dosimetric limits listed in section 8.3.4. All plans are expected to require no more than 2 hours per treatment, no more than 300 non-zero beams and no more than 95,000 monitor units for all fractions.

